6.2.5 Dose modification and delay

For patients who do not tolerate the protocol-specified dosing scheme, dose adjustments and interruptions are permitted. All dose modifications should be based on the worst preceding toxicity (CTCAE version 4.03). Once a dose reduction has occurred, the dose level may not be re-escalated during subsequent treatment cycles with INC280. In addition, in the Dose Determining Part, a patient must discontinue treatment with INC280 if, after treatment is resumed at a lower dose, the toxicity recurs with the same or worse severity. In the Dose Expansion Part, a patient must discontinue treatment with INC280 if, after treatment is resumed at the lowest allowed dose (200 mg BID, tablet), the toxicity recurs with the same or worse severity. All interruptions or modifications to study drug administration must be recorded on the Dose Administration Record eCRF.

If a dose delay of >21 days is required, then the investigational treatment with INC280 must be discontinued. [Table 6-3](#), [Table 6-4](#), [Table 6-5](#), [Table 6-7](#) and [Table 6-8](#) provide the guidelines to be followed for dose modification of the study drug in the event of toxicities. Included are

also instructions for re-initiation of study treatment once sufficient recovery of toxicity is seen. **Any dosing modifications that are not in accordance with the guidelines in Table 6-3, Table 6-4, Table 6-5, Table 6-7 and Table 6-8 (Andrew et al 2010) must be discussed with Novartis.** Any dose change to the study drug must be recorded on the eCRF. The study visit schedule should be followed irrespective of any study drug interruption.

In exceptional situations, study treatment may continue even if there is a dose interruption of >21 days or the patient experienced disease progression. The decision to allow for continuation of treatment will be made on a case-by-case basis following discussion between Novartis and the investigator. Situations that may allow for continuation of treatment include the following:

- A dose delay of >21 days has occurred but the patient is clearly benefiting from study treatment (i.e., SD, PR, or CR) and it is the investigator's opinion that no safety concerns are present.

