- A patient with disease progression may be allowed to continue study treatment if it is in the best interest of the patient to continue treatment. Examples of situations that may allow for continuation of therapy include cystic lesions, mixed responses, and new brain metastases that are treatable with stereotactic radiotherapy or surgery.

Table 6-3 and **Table 6-4** describe respectively for the Dose-Determining Part and Dose Expansion Part, the starting dose and the study drug dose modification to be followed in case of study drug related toxicities. For each patient in Dose Expansion Part treated with INC280 tablets, a maximum of 2 dose level modifications is allowed after which the patient must be discontinued from treatment. The lowest dose allowed, 200 mg BID in tablets is expected to be pharmacologically active, as the observed steady state plasma trough concentrations ([CINC280X1101], [CINC280X2202], n=6) were above the concentration associated with full cMET inhibition in xenograft mice models (EC90, 120 nM total concentration).

Table 6-3 Dose-Determining Part study drug dose reductions

Dose level	Dose and schedule (capsule)	Increment from previous dose
-1	200 mg bid	-33% of starting dose
0	300 mg bid	Starting dose for Dose-Determining Part

Table 6-4 Dose Expansion Part study drug dose reductions

Dose level	Dose and schedule (capsule)	Increment from previous dose
-1	450 mg bid (capsule)	-25% of starting dose
0	600 mg bid (capsule)	Starting dose for Expansion Part

Dose level	Dose and schedule (tablet)	Increment from previous dose
-2	200mg bid (tablet)	-50% of starting dose
-1	300 mg bid (tablet)	-25% of starting dose
0	400 mg bid (tablet)	Starting dose for Expansion Part

Table 6-5 Recommended dosing guidelines for study drug-related toxicities

Recommended dose modifications of INC280	
Worst toxicity CTCAE v4.03 grade	Recommended dose modifications any time during a cycle of therapy, including intended day of dosing
Hematologic	
ANC decreased (Neutropenia) Grade 1 (LLN - 1500/mm ³ or LLN – 1.5x10 ⁹ /L) Grade 2 (< 1500 - 1000/mm ³ or <1.5 – 1.0x10 ⁹ /L) Grade 3 (< 1000 - 500/mm ³ or < 1.0 – 0.5x10 ⁹ /L) Grade 4 (< 500/mm ³ or < 0.5x10 ⁹ /L)	Maintain dose level Maintain dose level Discontinue dose until resolved to ≤ grade 1 or baseline, then: If resolved in ≤ 7 days, then maintain dose level If resolved in > 7 days, then ↓ 1 dose level Discontinue dose and patient from study treatment.

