Grade 4 (>20.0 x ULN)	

Recommended dose modifications of INC280	
Worst toxicity CTCAE v4.03 grade	Recommended dose modifications any time during a cycle of therapy, including intended day of dosing
Combined ^b elevations of AST or ALT, and Total Bilirubin	
For patients with normal baseline ALT and AST and total bilirubin value: AST or ALT >3.0xULN combined with total bilirubin >2.0 x ULN without evidence of cholestasis ^c OR For patients with elevated baseline AST or ALT or total bilirubin value: [AST or ALT>2x baseline AND > 3.0 xULN] OR [AST or ALT > 8.0 xULN] combined with [total bilirubin >2x baseline AND >2.0 xULN]	Discontinue study treatment permanently. Repeat LFTs as soon as possible, preferably within 48 hours from awareness of the abnormal results, then with weekly monitoring of LFTs*, or more frequently if clinically indicated, until AST, ALT, or bilirubin have resolved to baseline or stabilization over 4 weeks. Refer to Section 6.2.6 for additional follow-up evaluations as applicable.
Reactivation of HBV or HCV	Please refer to Table 6-7 , Table 6-8 .
*LFTs include albumin, ALT, AST, GGT, total bilirubin (fractionated [direct and indirect] if total bilirubin > 2.0 x ULN) and ALP (fractionated [quantification of isoforms], if alkaline phosphatase > 2.0 x ULN). Refer to Section 6.2.6 for additional follow-up evaluations.	
Pancreatic^d	
Asymptomatic grade 1 or 2 amylase or lipase increased (>ULN – 2.0 x ULN)	Maintain dose level
Asymptomatic grade 3 or greater amylase or lipase increased (> 2.0 - > 5.0 x ULN)	Omit/delay dose until resolved to ≤ G2, then: If resolved in ≤ 7 days, maintain dose level If resolved in > 7 days, then ↓ 1 dose level
Asymptomatic grade 4 (> 5.0 x ULN)	Discontinue does and patient form study treatment
Symptomatic elevations of any grade	Discontinue does and patient form study treatment

Recommended dose modifications of INC280	
Worst toxicity CTCAE v4.03 grade	Recommended dose modifications any time during a cycle of therapy, including intended day of dosing
Neurologic	
Any Neurological Toxicity Grade 2	Discontinue study treatment. Neurological assessments must be repeated at least twice a week until resolution to < CTCAE grade 1. Unscheduled MRI and gadolinium enhanced T1 imaging may also be conducted to evaluate patients for intramyelinic edema like lesions, brain metastases and other unanticipated CNS occurrences. An EEG may be performed to monitor for physiological changes in brain activity.
Cardiac	

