Cardiac general Grade 1 or 2 Grade 3 Grade 4	Maintain dose level Discontinue dose until resolved to ≤ grade 1, then ↓ 1 dose level Discontinue dose and patient from study treatment
ILD / pneumonitis	
Monitor patients for pulmonary symptoms indicative of ILD/pneumonitis. In addition, withhold INC280 for acute onset of new or progressive unexplained pulmonary symptoms, such as dyspnea, cough and fever and during diagnostic workup for ILD/pneumonitis to exclude alternative causes such as, but not limited to infections, lymphangitic carcinomatosis, cardiogenic edema, or pulmonary hemorrhage.	
Grade 1	Interrupt INC280 during diagnostic workup for ILD/Pneumonitis. Exclude infections and other etiologies. In presence of diagnosis of ILD/Pneumonitis after diagnostic workup, it is mandatory to permanently discontinue INC280. Only in the absence of a diagnosis of ILD/Pneumonitis, INC280 may be restarted at the same dose. If it recurs after resumption of study drug, permanently discontinue INC280.

Recommended dose modifications of INC280	
Worst toxicity CTCAE v4.03 grade	Recommended dose modifications any time during a cycle of therapy, including intended day of dosing
Grade 2	
Mandatory: Interrupt INC280 dose during diagnostic workup for ILD/pneumonitis until improvement to \leq Grade 1. Exclude infections and other etiologies.
 
In presence of diagnosis of ILD/Pneumonitis after diagnostic workup, it is mandatory to permanently discontinue INC280.
 
Only in the absence of a diagnosis of ILD/Pneumonitis, INC280 may be restarted following these guidelines:
 
 · If resolves to \leq Grade 1 in \leq 7 days reduce study drug by 1 dose level · If fails to resolve to \leq Grade 1 within 7 days or recur after resumption of study drug at decreased dose, permanently discontinue INC280.
Grade 3 and Grade 4	Mandatory: Permanently discontinue INC280. Treat with IV steroids as clinically indicated. Oxygen therapy as indicated
Other adverse events	
Grade 1 or 2	Maintain dose level
Grade 3	Discontinue dose until resolved to \leq grade 1, then \downarrow 1 dose level
Grade 4	Discontinue study treatment

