
^a If total bilirubin $> 3.0 \times$ ULN is due to the indirect (non-conjugated) component only, and hemolysis as the etiology has been ruled out as per institutional guidelines (e.g. review of peripheral blood smear and haptoglobin determination), then \downarrow 1 dose level of INC280, and continue treatment at the discretion of the Investigator
 
^b "Combined" defined as: total bilirubin increase to the defined threshold concurrently with ALT/AST increase to the defined threshold
 
If combined elevations of AST or ALT and total bilirubin do not meet the defined thresholds, please follow the instructions for isolated elevation of total bilirubin and isolated elevation of AST/ALT, and take a conservative action based on the degree of the elevations (e.g. discontinue treatment at the situation when omit dose is needed for one parameter and discontinue treatment is required for another parameter). After all elevations resolve to the defined thresholds that allow treatment re-initiation, re-start the treatment either at the same dose or at one dose lower if meeting a criterion for dose reduction
 
^c "Cholestasis" defined as: ALP elevation ($>2 \times$ULN and R value <2) in patients without bone metastasis, or elevation of ALP liver fraction in patients with bone metastasis
 
Note : The R value is calculated by dividing the ALT by the ALP, using multiples of the ULN for both values. It denotes whether the relative pattern of ALT and/or ALP elevation is due to cholestatic (R\leq2), hepatocellular (R\geq5), or mixed (R>2 and <5) liver injury
 
^d A CT scan or other imaging study to assess the pancreas, liver, and gallbladder must be performed within 1 week of the first occurrence of any \geq Grade 3 of amylase or lipase.
	

Table 6-6 Follow-up evaluations for selected toxicities

Toxicity	Follow-up evaluation
Hematology	If febrile neutropenia of any duration occurs, the patient must be followed until resolution. If \geq CTCAE grade 3 hematologic toxicity occurs, the parameter must be repeated at least twice a week until resolution to \leq CTCAE grade 1 and then at least weekly until either initiation of retreatment or until stabilization.

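### As extracted, the neurologic stop rule in Protocol Table 6-5 names grade 2 only, so no dosing action is stated for grade 3 or 4; check the sign against the source page first

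*Protocol*

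**What the plan says.** Table 6-5 in Protocol Section 6.2.5 gives the dosing action for drug-related toxicity by CTCAE grade. Its neurologic section has one line, "Any Neurological Toxicity Grade 2". The action is to stop study treatment and repeat neurological assessments at least twice a week until the event falls below grade 1.

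Section 6.2.5 bases every dose modification on the worst preceding grade. It also sets two general limits:

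- "If a dose delay of >21 days is required, then the investigational treatment with INC280 must be discontinued", with exceptions agreed case by case with the sponsor.
- "Any dosing modifications that are not in accordance with the guidelines in Table 6-3" and in the other listed tables, Table 6-5 among them, must be discussed with the sponsor.

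Two other tables have a neurologic entry. Table 6-2 (Section 6.2.3) counts neurologic events of grade 2 or higher as qualifying adverse events for the dose decision. Table 6-6 starts neurologic follow-up at grade 2 or higher. Neither states a dosing action.

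**The concern.** The stop rule as printed covers the milder grade and is silent on the more severe ones. An investigator whose patient has a grade 3 neurologic event finds no neurologic line that matches. The nearest line that covers grade 3 is under "Other adverse events" in the same table, and it is more lenient than the neurologic stop at grade 2: hold until grade 1 or lower, then resume one level down.

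What is at stake is patient safety, in a small number of cases. The nonclinical summary (Section 1.2.1.1.3) reports tremors, convulsions and white matter vacuolation in the thalamus, in rats only and reversible. The stricter neurologic threshold in Table 6-2 fits that finding: most other adverse events qualify there only from grade 3. A stop rule that lapses at grade 3 does not fit it.

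**Working it through.** **1. The neurologic entries side by side**

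| Table | Purpose | Grade label as extracted | Monitoring endpoint |
|---|---|---|---|
| 6-2 | qualifying AE | ≥ grade 2 | not given |
| 6-5 | dosing action | grade 2, no sign | < grade 1 |
| 6-6 | follow-up | ≥ grade 2 | ≤ grade 1 |

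The monitoring text in Tables 6-5 and 6-6 is otherwise nearly identical. No other text in Section 6.2 gives a dosing action for grade 3 neurologic toxicity by name.

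**2. What follows if a site fills the gaps from the residual row**

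| Neurologic grade | Row used | Action |
|---|---|---|
| 1 | residual | maintain dose |
| 2 | neurologic | stop |
| 3 | residual | hold until ≤ grade 1, then one level lower |
| 4 | residual | stop |

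The only inversion is at grade 3. Table 6-5 words a temporary hold (discontinue the dose until resolved) differently from a permanent stop (discontinue study treatment), so the two actions do differ.

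**3. Size of the restart dose**

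The decrements printed in Tables 6-3 and 6-4 reproduce:

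- Tablets: 300/400 = 0.75, a 25% reduction.
- Expansion capsules: 450/600 = 0.75, a 25% reduction.
- Dose-Determining capsules: 200/300 = 0.667, a 33% reduction.

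On tablets, "a maximum of 2 dose level modifications is allowed after which the patient must be discontinued from treatment", so the steps are 400 to 300 to 200 mg bid. At grade 2 there is no restart at all.

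**4. Who is exposed**

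An event already recorded at grade 2 has met the stop rule. The exposed case is therefore an event that is first recorded at grade 3 and resolves to grade 1 or lower within 21 days, at a site that applies the residual row without asking the sponsor. The documents give no count of neurologic events, so no expected number can be calculated. The SAP introduction says that no patient was to be enrolled after 25-Dec-2016, which leaves patients still on treatment.

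**5. Can the missing sign be trusted?**

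- The sign ≥ does not occur in the extracted body of Table 6-5. The fever limit is printed there as >=38 °C, where Table 6-2 has ≥38 °C, and the pancreatic row spells out grade 3 or greater in words.
- The sign survives in the table's footnotes. In footnote d, imaging "must be performed within 1 week of the first occurrence of any" amylase or lipase elevation of ≥ grade 3. That shows it could be read from footnote text, not from the body.
- The signs ≤ and ↓ do survive in the body, which is some evidence against general loss of symbols.
- The neurologic row has a second mismatch, < in place of ≤. Two differing signs in one row fit local damage to characters.

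The extracted text cannot settle the question.

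**The case against.** The strongest objection is that this may be a single lost character. Tables broken in PDF reading are not errors in the plan, and the sign evidence in step 5 does not exclude that explanation. This stands. It lowers confidence and makes a check of the source page the first step.

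The second objection is that the intended rule is obvious. Tables 6-2 and 6-6 agree on grade 2 or higher, and an investigator told to stop at grade 2 is unlikely to be more lenient at grade 3. This also largely stands, but a dosing table should not need two other tables to be read correctly.

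Third, a reader might infer that the protocol permits restarting grade 3 neurologic patients while grade 2 patients must stop. The documents do not support that. No sentence assigns neurologic events to the residual row, and because Table 6-5 has a named neurologic section, the plain sense of other excludes them. Without that row no restart is authorised, and a modification outside the tables has to go to the sponsor. What remains is narrower. A site that believed the residual row applied would think it was following the tables and would see no need to call. The 21-day limit does not catch an event that resolves quickly.

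**Conclusion.** As extracted, Table 6-5 states no dosing action for grade 3 or 4 neurologic toxicity, and its label disagrees with the neurologic threshold in Tables 6-2 and 6-6. In practice only grade 3 matters, and only if a site uses the residual row; the cost is then a restart at a 25% lower dose (33% lower on Dose-Determining capsules) where a stop was evidently intended. A proven error in the protocol would be too strong a conclusion, because the sign may be present on the source page.

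Severity is low and confidence low to medium. Few patients are likely to be affected. The qualifying-AE analysis uses the threshold in Table 6-2. The primary time-to-progression analysis, including its censoring and analysis set, does not depend on this row.

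**What to change.** Check both signs in the neurologic row against the source page. If they are correct there, nothing needs to change. If they are absent:

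- Relabel the row: any neurological toxicity ≥ grade 2, discontinue study treatment.
- Write the monitoring endpoint as ≤ CTCAE grade 1, matching Table 6-6.

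The cost is a wording edit in one row, with no change to data collection or analysis. Section 12.1 requires a written amendment for any change, so the edit could go into the next one; Amendment 6 (16-May-2022) was still revising the toxicity guidance and provided for patients still on treatment. There are two downsides. Grade 3 patients lose a possible lower-dose restart that grade 2 patients are already denied. And a patient whose event settles at grade 1 would leave twice-weekly assessment earlier than the present wording of Table 6-5, read literally, requires.

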6.2.3 Adverse events criteria for dose decision analysis

As mentioned in [Section 4.1](#) and [Section 10.5.3.3](#), a two-parameter BLRM will be used for the safety analysis. This safety analysis (to be performed during the dose decision analysis after the Dose-Determining Part as well as to confirm the Expansion Part dose) will be based on data (occurrence/ absence) of certain AEs within 28 days treatment. The qualifying AEs are defined as an adverse event or abnormal laboratory value that is assessed by the investigator as related to therapy with INC280 and unrelated to disease progression, intercurrent illness, or concomitant medications and meets any of the criteria in [Table 6-2](#). The qualifying AEs will be considered in the safety analysis

Table 6-2 Criteria for qualifying AEs to be considered for the dose decision analysis

Toxicity	Any of the following criteria:
Hematology	Any grade 3 hematologic toxicity, lasting for > 7 consecutive days Grade 3 thrombocytopenia with bleeding Any grade 4 hematologic toxicity (of any duration) Febrile neutropenia (ANC < 1.0 x 10 ⁹ /L or 1000/mm ³ and a single temperature of >38.3 °C (101 °F) or a sustained temperature of ≥38 °C (100.4 °F) for more than one hour.
Renal	Serum creatinine ≥ grade 3 (≥3.0 x baseline or >3.0 - 6.0 x ULN)
Hepatic	≥ CTCAE grade 3 total bilirubin (> 3 x ULN) AST or ALT grade 3 (>5.0 -20.0 x ULN) for ≥ 7 consecutive days AST or ALT grade 4 (>20.0 x ULN) Reactivation of Hepatitis B or/and C
Pancreas	Asymptomatic ≥ CTCAE grade 3 serum amylase or lipase (>2.0 × ULN) occurring for > 14 consecutive days Symptomatic serum amylase or lipase elevation, medical intervention required
Neurologic	Any neurological abnormality or toxicity ≥ grade 2
Cardiac	≥ CTCAE grade 3

Toxicity	Any of the following criteria:
Other AEs	Any other AE \geq grade 3 Grade 3 fatigue, lasting for > 7 consecutive days Grade 3 nausea, vomiting, diarrhea if in setting of optimal, anti-emetic and anti-diarrheal therapy
CTCAE version 4.03 will be used for all grading. Patients may receive supportive care (e.g. transfusion of red blood cells) as per local institutional guidelines.	

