Renal	If serum creatinine \geq CTCAE grade 2 has been demonstrated, this parameter must be repeated at least twice a week until resolution to \leq CTCAE grade 1 or baseline, and then at least weekly until either initiation of re-treatment or until stabilization. Patients will be instructed to increase hydration until resolution to \leq CTCAE grade 1 or baseline.
Hepatic	In case of isolated elevations in total bilirubin, AST or ALT, additional follow-up evaluations are recommended as outlined in Table 6-9 .
Pancreatic	If serum amylase or serum lipase \geq CTCAE grade 3, follow until resolution to grade 2 or less.
Neurologic	If any neurological abnormality or toxicity \geq grade 2 has been demonstrated, neurological assessments must be repeated at least twice a week until resolution to \leq CTCAE grade 1. Unscheduled MRI and gadolinium enhanced T1 imaging may also be conducted to evaluate patients for intramyelinic edema like lesions, brain metastases and other unanticipated CNS occurrences. An EEG may also be performed to monitor for physiological changes in brain activity.
Cardiac	Monitor toxicity until resolution to grade 1 or baseline. If applicable, monitor electrocardiograms (ECGs) twice weekly until normalization or stabilization.
Non-laboratory	Patients who experience non-laboratory DLTs must be evaluated at least once a week following demonstration of the toxicity until resolution of the toxicity to allow for re-treatment, until stabilization of the toxicity, or until study completion.

Table 6-7 Guidelines for the management of hepatitis B reactivation

HBV-DNA OR HBsAg in baseline result	Definition of reactivation	Treatment
+	Increase of 1 log in HBV-DNA relative to baseline HBV- DNA value	
Provide antivirus treatment *
 
AND
 
Interrupt study drug administration until: ≤ baseline HBV-DNA levels
 
If resolution occurs within ≤ 21 days, study drug should be restarted at one dose lower, if available (see Table 6-2 and Table 6-3 for dose level available).
 
If the patient is already receiving the lowest dose of study drug according to the protocol, the patient should restart at the same dose after resolution.
 
If resolution occurs >21 days, patients should discontinue study drug but continue antiviral therapies at least 4 weeks after last dose of study drug.

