- / HBsAb (+) (with no prior history of vaccination against HBV or HBcAb(+)	New appearance of measurable HBV-DNA	
Provide antivirus treatment*
 
AND
 
Interrupt study drug administration until resolution: ≤ undetectable (negative) HBV-DNA levels
 
If resolution occurs within ≤ 21 days, study drug should be restarted at one dose lower, if available (see Table 6-2 and Table 6-3 for dose level available).
 
If the patient is already receiving the lowest dose of study drug according to the protocol, the patient should restart at the same dose after resolution.
 
If resolution occurs >21 days, patients should discontinue study drug but continue antiviral therapies at least 4 weeks after last dose of study drug.

*Antivirus treatment will be provided under discretion of investigator according to local clinical practice.

All reactivations of HBV are to be recorded as grade 3 (CTCAE version 4.03 Infections and infestations/Hepatitis viral), unless considered life threatening by the investigator, in which case they should be recorded as grade 4. Date of viral reactivation is the date on which the rise or reappearance of HBV-DNA criteria was recorded.

Table 6-8 Guidelines for the management of hepatitis C reactivation

HCV Reactivation*	
For patients with baseline results :	Discontinue INC280
Detectable HCV – RNA	
Reactivation is defined as :	
ALT elevation to > 5x ULN	
Increase of 1 log in HCV-RNA relative to baseline HCV-RNA value	
For patients with baseline results :	Discontinue INC280
Knowledge of past hepatitis C infection with no detectable HCV – RNA	
Reactivation is defined as :	
New appearance of detectable HCV – RNA	

* All reactivations of HCV are to be recorded as grade 3 (CTCAE Version 4.03 - Infections and infestations/Hepatitis viral), unless considered life threatening by the investigator, in which case they should be recorded as grade 4. Date of viral reactivation is the date on which the rise or reappearance of HCV-RNA (and ALT) criteria was recorded.

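### For a repeat HBV reactivation at the lowest dose, Table 6-7 and Section 6.2.5 give incompatible instructions; the table's dose pointer is wrong, and one of its triggers is undefined when baseline HBV-DNA is undetectable

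*Protocol*

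**What the plan says.** **Restart at the lowest dose.** Both rows of protocol Table 6-7 interrupt treatment at reactivation and allow a restart if it resolves within 21 days. For a patient with no lower level left: "If the patient is already receiving the lowest dose of study drug according to the protocol, the patient should restart at the same dose". The table sets no limit on how often this may happen.

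**Discontinuation on recurrence.** For the Dose-Determining Part, Section 6.2.5 states that "a patient must discontinue treatment with INC280 if, after treatment is resumed at a lower dose, the toxicity recurs with the same or worse severity". For the Expansion Part the same section attaches the rule to recurrence after resumption at the lowest allowed dose, named as 200 mg bid tablet. It also lists Table 6-7 among the guidelines to be followed.

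**Severity.** The note under Table 6-7 fixes the grade: "All reactivations of HBV are to be recorded as grade 3". The only exception is an event judged life threatening, which is recorded as grade 4.

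**Dose levels.** Both rows say "study drug should be restarted at one dose lower, if available (see Table 6-2 and Table 6-3 for dose level available").

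**Triggers.** Row 1 applies when either HBV-DNA or HBsAg is positive at baseline, and its trigger is "Increase of 1 log in HBV-DNA relative to baseline". Row 2 covers patients negative on both who carry the listed antibody markers, and its trigger is "New appearance of measurable HBV-DNA".

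**Use in the safety analysis.** Table 6-2 includes "Reactivation of Hepatitis B or/and C" among the hepatic criteria for a qualifying adverse event.

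**The concern.** A site managing a second reactivation at the lowest level cannot comply with both texts: one restarts the drug, the other ends it. Two sites could treat identical patients differently and each cite the protocol. Section 12 permits no authorized deviations, so following one text is a departure from the other.

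The pointer and the trigger raise the same kind of problem. The cited tables do not contain the expansion levels, and some row 1 patients will produce HBV-DNA results that the table cannot classify. Whether an event is recorded as a grade 3 reactivation then depends on an unstated local convention.

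Hepatitis B is not a marginal condition here. Section 1.1 calls it the most common etiology in the Asia-Pacific sorafenib study, and Section 2.2 takes that study as the design reference. The rules also remain in force: Amendment 6 provides for patients still on treatment, and Table 7-2 keeps hepatitis markers in the reduced schedule.

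**Working it through.** **1. Where the stop and restart texts collide**

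| Situation | Table 6-7 | Section 6.2.5 | Conflict |
|---|---|---|---|
| Dose-Determining Part: reactivation at 300 mg bid capsule, resumed at 200 mg, reactivates again | Restart at 200 mg | Must discontinue | Yes |
| Expansion, tablets: resumed at 200 mg bid after reactivation, reactivates again | Restart at 200 mg | Must discontinue | Yes |
| First reactivation in a patient at the lowest level because of another toxicity | Restart at same dose | Recurrence rule not met | Not shown |
| Expansion, capsules at 450 mg bid | Restart at same dose | Recurrence rule names only the 200 mg tablet | Not shown |

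The severity condition is nearly always met. Every reactivation is grade 3 or grade 4, so the second is less severe than the first only when a grade 4 event is followed by a grade 3 event.

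No precedence rule covers the case. Appendix 4 lets the stricter drug table govern, and footnote b of Table 6-5 asks for conservative action on combined liver elevations; neither applies to Table 6-7. The exceptional-continuation clause in Section 6.2.5 concerns interruptions longer than 21 days and disease progression, not recurrent toxicity.

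Section 6.2.5 also limits expansion tablet patients to two level modifications. This would widen the conflict only if the limit were read as covering any later toxicity that calls for a reduction, so the point does not rely on it.

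**2. The dose pointer**

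The stated decrements reproduce as level / start − 1:

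- Table 6-3, capsule: 200/300 − 1 = −33.3% (stated −33%).
- Table 6-4, capsule: 450/600 − 1 = −25.0% (stated −25%).
- Table 6-4, tablet: 300/400 − 1 = −25.0% and 200/400 − 1 = −50.0% (stated −25% and −50%).

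Table 6-2 contains no dose levels. Table 6-3 is titled for the Dose-Determining Part and shares no level with Table 6-4 once formulation is counted: its 200 mg bid is a capsule dose, whereas the 200 mg bid in Table 6-4 is a tablet dose. The pointer therefore omits every expansion level.

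**3. The row 1 trigger with undetectable baseline HBV-DNA**

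A patient who is HBsAg-positive with undetectable HBV-DNA falls in row 1, because the selector needs only one of the two to be positive. Section 6.3.1 permits antivirals for HBV, so this profile is plausible; the documents do not give its frequency. Section 7.2.2.5.5 monitors HBV-DNA in such patients on Day 1 of each cycle from Cycle 2 and at end of treatment.

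The trigger is log10(follow-up) − log10(baseline) ≥ 1. With baseline 0, log10 is undefined. The documents give no HBV-DNA detection limit and no substitution rule. If an undetectable value were replaced by L, the threshold would be 10 × L. The values of L below are assumptions:

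| Assumed L (IU/mL) | Threshold (IU/mL) |
|---|---|
| 1 | 10 |
| 10 | 100 |
| 20 | 200 |
| 100 | 1000 |

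That is a 1000/10 = 100-fold range set by a convention the protocol does not state. In row 2 any newly measurable HBV-DNA counts. The same new result is therefore a reactivation in a row 2 patient and undetermined in this row 1 patient.

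**The case against.** The best defence is that the two texts can be read together. Table 6-7 is a guideline worded with *should*, and it covers any reactivation at the lowest dose, including a first one. Section 6.2.5 is worded with *must* and covers recurrence only. On that reading the section governs repeats and the table governs the rest. This correctly narrows the conflict to repeat events, but the protocol does not state the ordering, and Section 6.2.5 itself tells sites to follow Table 6-7.

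On the pointer, Section 6.2.5 cites Table 6-4 elsewhere and assigns Tables 6-3 and 6-4 to their respective parts, so a careful site would find the right levels. A reader might infer that the error sends a 600 mg bid patient to 200 mg bid, a cut of (600 − 200)/600 = 67%. That requires ignoring the title and starting dose of Table 6-3, which has no 600 mg level; the next lower figure in it is equally 300 mg, a 50% cut. The pointer is a cross-reference error, not a competing dose rule.

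On the trigger, a stated substitution value would make it computable, so the gap is in the text and not in principle. It would also be wrong to say that row 1 lacks a resolution rule. Return to baseline HBV-DNA or below is workable, and for an undetectable baseline it means undetectable.

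A reader might also infer that a miscounted reactivation could move the expansion dose, since Table 14-18 shows 0/6, 1/6 and 2/6 leading to 600, 500 and 300 mg bid. The documents do not support that as a live consequence. The Amendment 2 study update reports the Dose-Determining Part complete, and the SAP introduction reports expansion enrollment permanently halted after 25-Dec-2016. Table 14-18 is hypothetical and model-only, and a qualifying event must also be judged related to INC280. Of the scheduled HBV-DNA readings, only Cycle 2 Day 1 (day 21 + 1 = 22) falls in the 28-day window; the next is day 43.

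**Conclusion.** The concern holds in a limited form: these are inconsistencies of text, and three parts stand.

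- **Stop versus restart:** a direct contradiction for a repeat reactivation after resumption at 200 mg bid capsule (Dose-Determining Part) or 200 mg bid tablet (Expansion Part). It assumes the second event is not milder than the first, which the grading note makes true except for grade 4 followed by grade 3. It is not shown for a first reactivation at the lowest level, nor at 450 mg bid capsule.
- **Pointer:** a plain error, present in both rows.
- **Trigger:** undefined from the protocol text for HBsAg-positive patients with undetectable baseline HBV-DNA. The 100-fold range rests on assumed substitutes of 1 to 100 IU/mL; the number of such patients is unknown.

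The first part matters most, because it concerns whether a patient stays on drug after a repeated safety event. No effect on the completed dose decision, on time to progression or on its analysis is claimed. No view is taken on which clinical rule is right.

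**What to change.** 1. Reconcile Table 6-7 with Section 6.2.5 so that one instruction applies to a repeat HBV reactivation at the lowest dose, and state which text governs if both remain.
2. In both rows of Table 6-7, replace the reference to Tables 6-2 and 6-3 with Tables 6-3 and 6-4, by study part.
3. Reconcile the triggers in the two rows so that reactivation can be determined for an HBsAg-positive patient whose baseline HBV-DNA is undetectable.

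The clinical content of items 1 and 3 is for the sponsor to decide. The cost is amended wording in one table and one paragraph, with the usual amendment approvals. No new assessments are needed, since HBV-DNA is already monitored, and no planned analysis changes.
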